6.4.1.4 Subgroup Analysis for Primary and Secondary Efficacy Endpoint

Primary and secondary efficacy endpoints will be analyzed as in Section 6.4.1.1 for the following subgroups:

| Grouping variable | Subgroups |
|--------------------------|-------------------------|
| Age groups | 1 to < 12 years of age |
| | 12 to < 18 years of age |
| Organism | IA |
| | IM |
| | Mixed IA/IM |
| | Other |

Site of Infection

Considered ad hoc depending on number of sites.

6.4.2 Analysis of Key Secondary Efficacy Endpoints

The key secondary efficacy endpoints will be all-cause mortality through day 84 and EOT. The crude mortality rate will be calculated by dividing the number of deaths by the number of FAS and mFAS subjects, and a 2-sided 95% exact CI will be calculated. All deaths, which occurred on Day 1 (after initial dosing) to days 84 and EOT.

6.4.2.1 Other Analysis of Key Secondary Efficacy Endpoint(s)

Rate of death over time will be estimated using K-M which will generate a survival function from Day 1 through 84 and for Day 1 through EOT. A subject observed to endpoint time, and without reported death, will be censored on the subject's last assessment day. The cumulative probabilities of mortality rates (100%-survival rates) by the end of study will be presented. K-M curve for time to death will be generated.

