End of Treatment (EOT)	The date the last dose of study drug was taken by the enrolled subject. In this study, the end of treatment is a maximum of 84 days for invasive aspergillosis subjects or 180 days for invasive mucormycosis subjects.
Endpoint	Variable that pertains to the efficacy or safety evaluations of a trial.
Enroll	To register or enter a subject into a clinical trial. Note: Once a subject has received the study drug, the clinical trial protocol applies to the subject.
Evaluable Subject	A subject who has received at least one dose of study drug.
Intervention	The drug, device, therapy or process under investigation in a clinical study that is believed to have an effect on outcomes of interest in a study. (e.g., health-related quality of life, efficacy, safety and pharmacoeconomics).
Screen failure	Potential subject who did not meet 1 or more criteria required for participation in a trial.
Screening	A process of active consideration of potential subjects for enrollment in a trial.
Screening period	Period of time before entering the investigational period, usually from the time when a subject signs the consent until just before the test drug is given to a subject.
Study period	Period of time from the first site initiation date to the last site completing the study.
Variable	Any entity that varies; any attribute, phenomenon or event that can have different qualitative or quantitative values.

IV. SYNOPSIS

Date and Version # of Protocol Synopsis:	05 Sep 2019 / Version 4.0
Sponsor: Astellas Pharma Global Development Inc. (APGD)	Protocol Number: 9766-CL-0107
Name of Study Drug: Isavuconazonium sulfate	Phase of Development: 2
Title of Study: A Phase 2, Open-Label, Non-Comparative, Multicenter Study to Evaluate the Safety and Tolerability, Efficacy and Pharmacokinetics of Isavuconazonium Sulfate for the Treatment of Invasive Aspergillosis (IA) or Invasive Mucormycosis (IM) in Pediatric Subjects	
Planned Study Period: From 1Q2019 to 1Q2021	
Study Objective(s): Safety Objective To evaluate the safety and tolerability of isavuconazonium sulfate in pediatric subjects Efficacy Objective To assess the efficacy of isavuconazonium sulfate for the treatment of invasive aspergillosis (IA) or invasive mucormycosis (IM) in pediatric subjects Pharmacokinetic Objective To evaluate the pharmacokinetics of isavuconazole by monitoring the plasma concentrations in pediatric subjects during treatment with isavuconazonium sulfate	

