2.2 Study Design

This is a phase 2, open-label, non-comparative, multicenter study to assess the safety, efficacy and pharmacokinetics of isavuconazonium sulfate in pediatric subjects for the treatment of IA or IM.

An approved informed consent form (ICF) must be obtained from the subject’s parent or legal guardian, and, if required, child assent prior to any study related procedures being performed.

Approximately 30 centers in the United States (US) and European Union (EU) are planned to enroll approximately 30 subjects ages 1 to < 18 years of age

The subjects will enter into screening anytime between days -5 to day 1 (predose). All subjects will be assigned to open-label treatment. Treatment will begin on day 1 and then subjects are followed for 60 days after the last dose for safety. Treatment will be administered until the subject has a successful outcome as judged by the investigator or for a maximum duration of 84 days (IA) or 180 days (IM), whichever occurs first.

After successful screening, all subjects will receive a loading regimen of isavuconazonium sulfate, which consists of a dose every 8 hours (\pm 2 hours) on days 1 and 2 (for a total of 6 doses), followed by once daily maintenance dosing for up to 84 days (IA) or day 180 (IM) of dosing. The first maintenance dose should start 12 to 24 hours after the administration of the last loading dose. Subsequent maintenance doses will be administered once daily (24 hours \pm 2 hours from the previous maintenance dose).

Blood sampling for the analysis of trough levels will be obtained from all subjects. The samples should ideally be drawn immediately prior to the next dose of study medication, but must be taken no earlier than 1 hour prior to the next dose on days 7, 14, 21, 42 and 84 or end of treatment (EOT). **In addition to the above, 24-hour pharmacokinetic samples will be obtained on any day between day 14 and day 42, while the subject is still receiving study drug, for subjects that consent to participation in the 24-hour pharmacokinetic assessment.** No additional samples are taken from IM subjects between day 84 through day 180.

Throughout the study, safety and tolerability will be assessed by the recording of AEs, vital signs, electrocardiograms (ECGs) and safety laboratory evaluations. All subjects will complete 2 follow-up visits (via telephone at the discretion of the investigator), 30 and 60 days, after the subject's day 84 (IA) /day 180 (IM) or EOT visit.

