6 STATISTICAL METHODOLOGY

6.1 General Considerations

Continuous data will be summarized descriptively including the number of subjects (n), mean, standard deviation (SD), median, minimum and maximum. Categorical data will be summarized by frequencies and percentages with 95% confidence interval (CI). Efficacy data will be summarized by type of infection including IA, IM and mixed IA/IM infected subjects. Safety summaries will also be presented for by type of infection. The IA group will comprise subjects with IA infection without known IM infection; the IM group will comprise subjects with IM without known IA infection; and the IA/IM group will comprise subjects with mixed IA/IM infection. Analysis Windows will be used and, for those parameters with weekly data collection, are illustrated below in Section 6.9. For those parameters collected less often appropriate windows will be defined. Note that, IM and IA/IM infected subjects will be reported to conclusion of treatment and 60 day follow-up although day 180 is not considered an endpoint analysis. Kaplan Meier (K-M) analyses for mortality will incorporate all survival data to day 240 if IM subjects are included.

All data summarization and analyses will be performed using SAS® Version 9.1.3 or higher. Specifications for table, figures and data listing formats can be found in the Tables, Listings, and Figures (TLF) specifications.

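### The Kaplan-Meier curve to end of treatment in SAP 6.4.2.1 does not estimate mortality through EOT, whichever way its censoring rule is read

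*SAP*

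**What the plan says.** The key secondary endpoint is all-cause mortality through Day 84 and EOT. SAP 6.4.2 estimates it as a proportion with an exact 95% CI: "The crude mortality rate will be calculated by dividing the number of deaths by the number of FAS and mFAS subjects". SAP 5.2.2.1 counts a child lost to follow-up as a death.

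SAP 6.4.2.1 then adds a K-M analysis, "which will generate a survival function from Day 1 through 84 and for Day 1 through EOT". Its censoring rule is: "A subject observed to endpoint time, and without reported death, will be censored on the subject's last assessment day". Its read-out is: "The cumulative probabilities of mortality rates (100%-survival rates) by the end of study will be presented". SAP 6.1 says that K-M "analyses for mortality will incorporate all survival data to day 240 if IM subjects are included".

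The protocol's Definition of Key Study Terms gives EOT as "The date the last dose of study drug was taken by the enrolled subject". SAP 2.2 states: "Treatment will be administered until the subject has a successful outcome as judged by the investigator", with a maximum of 84 days (IA) or 180 days (IM). Protocol 6.1 lists further reasons for stopping, such as an adverse event or an investigator decision, and keeps those children in the study. SAP 2.2 plans contacts 30 and 60 days after EOT. The SAP names no competing-risk method, and SAP 6.4 rules out formal inference.

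**The concern.** The endpoint through EOT counts a death only if it occurs up to that child's last dose. Once a child reaches EOT alive, for whatever reason, the event can no longer happen. K-M censoring assumes the opposite: the child stays exposed to the event and carries the same later risk as the children still on drug. A curve whose time axis ends at a different day for each child therefore does not give the proportion who died through EOT.

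Following the children past EOT does not repair this, because deaths after EOT then enter the figure. The report could show two mortality figures for one key secondary endpoint that differ because of the method, with nothing in the SAP to explain the difference.

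**Working it through.** The plan gives no expected mortality rate or sample-size formula, so there is no figure of its own to reproduce. Inputs from the documents are N of about 30 (SAP 3) and 30% mortality at 12 weeks in a cited paediatric cohort (Protocol 1.1). Rates of early stopping and of loss are assumptions, because the documents give none.

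**1. Why the two figures differ if survivors are censored at EOT.** At a death on day t the K-M curve drops by S(t-)/n(t), where n(t) is the number at risk. With no earlier EOT, n(t) = N × S(t-) and the drop is 1/N. Each earlier EOT alive lowers n(t) but not S(t-), so the drop exceeds 1/N. With complete follow-up, 1-KM is therefore at or above deaths/N, and above it whenever a death follows another child's earlier EOT.

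**2. Worked example.** N=30; deaths on days 10, 25, 40, 55, 65 and 75; 14 children stop alive on days 28, 30, 35, 38, 42, 45, 48, 50, 52, 56, 58, 60, 62 and 70; ten reach Day 84; none is lost. The numbers at risk at the six deaths are 30, 29, 24, 18, 13 and 11.
- S = (29/30)(28/29)(23/24)(17/18)(12/13)(10/11) = 0.709, so 1-KM = 29.1%.
- Crude = 6/30 = 20.0% (exact 95% CI 7.7% to 38.6%).
- With no early stops, or with all six deaths before the first stop, both figures are 20.0%.
- A cumulative incidence function with EOT alive as the competing event drops by exactly 1/30 at each death and gives 20.0%.

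**3. Size at 30% mortality, no loss.** Assume 30% die by Day 84, evenly spread over time. A fraction f of the survivors stops evenly over Days 14 to 84, and none of these would have died. Put s = 0.70f. By Day 14, 0.30 × 14/84 = 5% have died. Over the next 70 days 25% die and s stop, so the fraction at risk falls in a straight line from 0.95 to 0.70 - s. Then 1-KM = 1 - 0.95 × [(0.70 - s)/0.95]^(0.25/(0.25 + s)).

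| f | s | 1-KM | Excess over 30% |
|---|---|---|---|
| 0 | 0 | 30.0% | 0 |
| 0.25 | 0.175 | 33.0% | +3 points |
| 0.50 | 0.350 | 37.3% | +7 points |
| 0.75 | 0.525 | 45.0% | +15 points |

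Simulation at N=30 agrees for evenly spread deaths (37.3% and 44.8% at one half and three quarters). With deaths mostly early it gives about +1 point at one quarter, 32.7% at one half and 35.4% at three quarters. For scale, the standard error of the crude rate is sqrt(0.30 × 0.70/30) = 8.4 points.

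**4. If stopping is unrelated to the risk of death.** In simulation with constant hazard and 30% mortality by Day 84, 1-KM stays near 30% while the crude through-EOT rate is 27.0%, 24.7% and 22.7% with 30%, 50% and 70% stopping early. The gap is 3 to 7 points, but it arises because the crude rate falls.

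**5. If children are followed past EOT.** Assume constant hazard, EOT at Day 84 and follow-up to EOT + 60, which is Day 144. A Day 84 mortality of 10%, 20% or 30% becomes 1 - 0.90^(144/84) = 16.5%, 1 - 0.80^(144/84) = 31.8% or 1 - 0.70^(144/84) = 45.7% by the end of follow-up. The excess consists of deaths after EOT.

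**6. Loss to follow-up.** Take six deaths, all before the first stop, and three children lost after the last death. The crude rate is (6 + 3)/30 = 30.0%, while 1-KM is 6/30 = 20.0%. In the example of step 2 with three further children lost on days 20, 50 and 60 instead of reaching Day 84, the crude rate is 9/30 = 30.0% and 1-KM is 34.2%. The sign depends on the timing of deaths and on the amount of loss.

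**The case against.** The strongest reply is that censoring at EOT is not written down. The rule refers to an undefined last assessment day, SAP 6.1 brings in survival to Day 240 when IM subjects are included, children stay in the study after stopping drug, and the figure is read at end of study. On that reading, stoppers stay in the risk set and the competing-event mechanism does not operate. This stands as far as it goes, and it makes the first mechanism conditional. It does not rescue the analysis, because the curve then counts post-EOT deaths (step 5). The Day 240 sentence also does not settle a curve for IA alone.

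A reader might infer that K-M always overstates the key secondary rate. The documents do not support that: the crude rate counts losses as deaths and the K-M does not, so the net difference can be negative. There is also no gap when every death precedes the first stop.

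A reader might also infer that the drug would look worse because it works sooner. That needs early stoppers to be children who would not have died. If stopping is unrelated to risk, early stopping leaves 1-KM unchanged (step 4). The documents also do not say that most stops are for success, or that those still on drug are non-responders.

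Finally, the curve is an additional descriptive analysis and no decision rests on it. That is correct and limits the weight of the point.

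**Conclusion.** The point holds in conditional form. On neither available reading is 1-KM from the through-EOT curve the proportion who die through EOT. This is a wrongly specified analysis as well as an undefined term.

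With censoring at EOT and complete follow-up, the excess over deaths/N is about 3 to 15 points if half to three quarters of survivors stop early, and 1 to 3 points if a quarter do. These sizes assume N=30, 30% mortality and stoppers who would not have died. The upper end also needs evenly spread deaths and three quarters stopping early. The different handling of losses is a second mismatch that can offset or reverse the first.

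It would be wrong to conclude that the key secondary result is biased. The crude rate in SAP 6.4.2 and its exact CI do not use the curve. The change is worth making because it is cheap and prevents two unexplained mortality figures for one endpoint.

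**What to change.** - In SAP 6.4.2.1, delete the through-EOT curve and report mortality through EOT as the crude proportion with exact CI already planned. If a curve is wanted, use a cumulative incidence function (Aalen-Johansen) with EOT reached alive as the competing event.
- Keep K-M for Day 1 to 42 and Day 1 to 84. Define the censoring date as the last date known alive, including contacts after EOT, and not EOT itself.
- Replace the end-of-study read-out with the fixed day of each curve, and reconcile this with the Day 240 sentence in SAP 6.1.
- Either state beside the results that the K-M censors losses while the crude rate counts them as deaths, or align the two.

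The cost is SAP wording and minor programming, with no new data. One K-M figure is dropped or replaced.

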6.4.3 Analysis of Additional Secondary Efficacy Endpoints

Additional secondary efficacy endpoints will be overall, clinical, radiological and mycological response through day 42, day 84 and EOT. AC will assess all endpoints, Investigator's assessment include all endpoints except the overall response.

Each endpoint with the assessment criteria defined below will be summarized descriptively for FAS and mFAS populations through day 42, day 84 and EOT. Frequencies and 95% CI will be reported. All data will be represented in Listings by subject.

6.4.3.1 Investigator-assessed Clinical Response

| Category | Outcome |
|-----------------|--|
| Success | 
resolution of all attributable signs and symptoms OR |

| | |
|---------------|---|
| | 
 resolution of attributable clinical symptoms and physical findings |
| Failure | 
 no resolution of any attributable signs and symptoms OR no resolution of any attributable signs and symptoms (no change) or worsening of any attributable signs and symptoms |
| Not Evaluable | 
 Results not available /subject unevaluable OR No attributable signs and symptoms |

6.4.3.2 Investigator-assessed Mycological Response

| Category | Outcome |
|--|---|
| Success | 
 Eradicated Presumed Eradication |
| Failure | 
 Persistence Presumed persistence |
| Not Evaluable | 
 Indeterminate No Mycological Follow-up Results Available |
| No Mycological evidence at screening (up to day 104) | Remains as is |
| No baseline signs, not applicable for response. | Remains as is |

6.4.3.3 Investigator-assessed Radiological Response

| Category | Outcome |
|---------------|--|
| Success | 
 ≥ 90% improvement ≥ 50% to < 90% improvement ≥ 25% to 50% improvement (for Day 42 only) |
| Failure | 
 < 25% improvement at any time No Signs or Radiological Images |
| Not Evaluable | 
 Results Not Evaluable No Radiological Data Available |

6.4.3.4 AC-assessed Clinical Response

Clinical response will be defined as follows:

| Summary | Category | Outcome |
|---------|----------|--|
| Success | Complete | 
 Resolution of all attributable clinical symptoms and physical findings |

| | | |
|---------------|---|--|
| | Partial | 
 Resolution of at Least some of the clinical symptoms and physical findings associated with IFD |
| Failure | Stable | 
 Minor or no change in clinical symptoms and physical findings associated with IFD |
| | Progression | Worsening or new clinical symptoms and physical findings associated with IFD, or if alternative systemic antifungal treatment is required |
| Not Evaluable | Not Assessed | |
| | No clinical signs or symptoms at baseline | |

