5.1.2 Previous and Concomitant Treatment (Medication and Nonmedication Therapy)

Systemic antifungal medications taken for IM or IA or suspected mycoses and other medication taken within 28 days prior to the screening visit and up to the first dose of study

drug (investigational period) will be documented as prior antimycotic medications or other prior medication, respectively.

Medications taken after the first dose of study drug and up to EOS will be documented as concomitant medications.

Prior and concomitant medications and nonmedications to be documented include, but are not limited to, the following: vitamins, herbal remedies (e.g., St. John's Wort, valerian) and over-the-counter and prescription medications. Any medications taken for treatment of pain symptoms will be documented as such.

Subjects are instructed not to take any concomitant medication without first consulting the investigator or study coordinator throughout the duration of the study.

Prohibited Therapies:

Treatments with concomitant drugs that are strong inhibitors or inducers of CYP3A4 are prohibited, including ketoconazole, high dose ritonavir, rifampin/rifampicin, carbamazepine and St. John's Wort or long acting barbiturates (e.g., phenytoin). Concomitant use of sirolimus, atorvastatin, cyclosporine, tacrolimus, midazolam, bupropion, mycophenolate mofetil and digoxin should be made with caution.

Treatments with concurrent drugs that are CYP3A4 substrates and have a narrow therapeutic range (e.g., vincristine) should be used with caution, and if clinically warranted, consider reduction of substrate dose.

Use of other systemic antifungals is prohibited during study drug administration.

Subjects taking prohibited medications who are willing to discontinue these medications, as clinically indicated and based upon the investigator's recommendation, may washout over a period of 5 half-lives on a schedule determined by the investigator.

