6.4.3.5 AC-assessed Mycological Response

| | Category | Outcome |
|---------------|-------------------------|--|
| Success | Eradication | No growth of the original (at baseline) causative organism on culture or identified by histology/cytology on post baseline (after day 7) cultures and/or histology/cytology |
| | Presumed eradication | Missing post baseline documentation of eradication of the original causative organism at baseline PLUS resolution of all or some clinical symptoms/physical finding |
| Failure | Persistence | Persistence of the original causative organism cultured or identified by histological /cytology at baseline or ?? |
| | Presumed Persistence | Missing post baseline documentation of the persistence of the original causative organism at baseline PLUS no resolution or worsening of any clinical symptoms/physical findings |
| Not Evaluable | No Mycological Evidence | |

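### Needing another systemic antifungal is a failure only in AC clinical response; at Day 42 and Day 84 other response endpoints can score the same child a success, and AC overall response does not say

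*SAP*

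**What the plan says.** SAP 5.2.2.2 lists clinical, radiological and mycological response, each assessed by both the Adjudication Committee (AC) and the investigator, plus AC overall response. The time points are Day 42, Day 84 and EOT. Protocol 7.4.2.2 reports crude success rates with exact 95% CIs in the FAS and mFAS.

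Only SAP 6.4.3.4 (AC clinical) refers to another antifungal. Its Progression category, a Failure, covers "Worsening or new clinical symptoms and physical findings associated with IFD, or if alternative systemic antifungal treatment is required".

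The investigator's clinical response (6.4.3.1) rests on findings alone. Success includes "resolution of all attributable signs and symptoms", and Failure includes "no resolution of any attributable signs and symptoms (no change) or worsening of any attributable signs and symptoms".

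AC mycological response (6.4.3.5) allows success by presumption: "Missing post baseline documentation of eradication of the original causative organism at baseline PLUS resolution of all or some clinical symptoms/physical finding".

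Protocol 5.1.2 states: "Use of other systemic antifungals is prohibited during study drug administration". Protocol 6.1 keeps children who stop treatment in the study. The protocol's key terms define EOT as the date of the last dose of study drug.

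**The concern.** Other systemic antifungals are barred while study drug is given, so rescue normally follows an early stop. The child stays in follow-up, and Day 42 and Day 84 response are time points in their own right, not limited to time on study drug. A response read then may be a response to the second drug.

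The SAP recognises this in one endpoint only. AC and investigator clinical response are listed together as the same kind of endpoint, yet they can score the same course in opposite directions for a reason unrelated to who assessed it. In a single-arm trial no comparator separates the two drugs' effects, so recovery on the second drug would be credited to isavuconazonium sulfate.

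**Working it through.** **Step 1. Can the situation arise at Day 42 and Day 84?** Follow-up runs for 60 days after the last dose (Protocol 2.2.1). A child stopping on day *d* is followed to about day *d* + 60.
- Day 42 falls inside follow-up for every early stopper, since even *d* = 1 gives Day 61.
- Day 84 falls inside it when *d* ≥ 84 − 60 = 24, before visit windows.
- EOT is the last-dose date, so recovery on a drug started later should not reach it. The exceptions are the visit window and a deviation with concurrent antifungals.

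**Step 2. The seven definitions side by side.** The test case is constructed. The child has a baseline organism, stops study drug on Day 10 and requires another mould-active drug for the baseline infection. Symptoms then resolve by Day 42, and no culture is repeated.

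| Endpoint (SAP section) | Antifungal clause? | Score at Day 42 |
|---|---|---|
| AC clinical (6.4.3.4) | Yes: "or if alternative systemic antifungal treatment is required" | Failure |
| Investigator clinical (6.4.3.1) | No | Can be Success |
| AC mycological (6.4.3.5) | No | Can be Success by presumed eradication; presumed persistence does not fit, as it needs symptoms unresolved or worse |
| Investigator mycological (6.4.3.2) | No; failure is persistence or "Presumed persistence" | Success if judged presumed eradication (not defined there); Not Evaluable if classed as lacking follow-up results |
| Investigator radiological (6.4.3.3) | No; failure includes "< 25% improvement at any time" | Success if images improve enough; Not Evaluable with no images |
| AC radiological (6.4.3.6) | No | Success if images improve enough; Not Evaluable with no post-baseline images |
| AC overall (6.4.3.8) | No | Undefined: labels only, no rule for combining components |

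One endpoint of seven carries the rule, five can score Success, and one is undefined.

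**Step 3. Is it handled elsewhere?** SAP 6.4.1.3 removes mFAS patients on excluded medication for fungal disease from a sensitivity analysis of the primary endpoint, Day 42 mortality. It does not score them as failures and does not touch response. The same section makes death by Day 42 override an AC overall success, but gives no matching rule for rescue.

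**Step 4. Size.** The plan gives no target response rate and no rescue rate, so there is no stated figure to reproduce. Taking the whole analysis set as denominator, each affected child moves a rate by 1/N:
- N = 30 (planned): 1/30 = 3.3 points.
- N = 25 (evaluable minimum in Protocol 2.2.1): 1/25 = 4.0 points.
- N = 15 (assumed smaller subset): 1/15 = 6.7 points.

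For illustration, assume 15 of 30 succeed without rescue and *k* more recover on another drug. The exact (Clopper-Pearson) limits are the 2.5% quantile of Beta(x, n − x + 1) and the 97.5% quantile of Beta(x + 1, n − x).

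| *k* scored Success | Rate | Exact 95% CI |
|---|---|---|
| 0 | 15/30 = 50.0% | 31.3–68.7 |
| 1 | 16/30 = 53.3% | 34.3–71.7 |
| 3 | 18/30 = 60.0% | 40.6–77.3 |
| 6 | 21/30 = 70.0% | 50.6–85.3 |

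Both the 15/30 base and *k* are assumptions.

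**The case against.** Several points on the other side stand and limit the conclusion.

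- **Overall response.** A reader might infer that a rescued child is a success on every other endpoint, overall response included. The SAP does not support that. The AC may carry clinical Progression into the overall result, and its operating procedures are in a separate charter (Protocol 10.2) that is not available here.
- **Culture and imaging.** Success there is possible, not automatic. After an early stop the scheduled contacts are the EOT procedures and two follow-ups that may be by telephone. For a Day 10 stop these fall near Days 40 and 70. Table 1, footnote 7 asks only that assessments which are performed be recorded.
- **Reason for the switch.** A reader might infer that any switch is an AC clinical failure. The clause says the other treatment must be required, and it sits under Progression. A child switched for intolerance while the infection improves is not clearly covered.
- **Transparency.** Excluded concomitant treatment is a listed deviation (PD4), systemic antifungals are reported separately (SAP 6.2.6), and response is listed by subject. With about 30 children a careful reader could find these cases.
- **Stakes.** These are additional secondary endpoints in a descriptive trial.

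None of this reconciles the two clinical response definitions. Listings let a reader find the cases but do not correct the reported rates. The SAP writes out its own response criteria, and an AC charter would not govern the investigator's assessments.

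**Conclusion.** The inconsistency is real and can be read directly from SAP 6.4.3.1 to 6.4.3.8. At Day 42 and Day 84, a child needing another antifungal is a Failure on AC clinical response. That child can be a Success on investigator clinical response and on AC mycological response by presumption. The radiological and investigator mycological endpoints can also give Success if their criteria are met, and AC overall response is unspecified. EOT response is largely untouched.

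The firm figure is 3.3 points per affected child at N = 30. A reader might take the 10- or 20-point shifts for 3 or 6 children as an expected bias; the documents support no such estimate, because they give neither the number of rescued children nor a base rate. No alpha or power is affected. The point merits correction because the rates are reported efficacy results, there is no comparator, and the change is mostly wording.

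**What to change.** 1. Apply the 6.4.3.4 rule to investigator clinical response: another systemic antifungal required for the baseline fungal disease on or before the time point is Failure at that time point. State in 6.4.3.8 that this carries into AC overall response.
2. In 6.4.3.5, let presumed eradication rest only on clinical resolution that occurred before such treatment.
3. Keep observed culture and imaging results as found. Add supportive rates: mycological and radiological with rescued children counted as failures, and clinical and overall ignoring rescue.
4. Reconcile Protocol 5.1.2, which documents medications up to end of study, with Table 1 footnote 13, Table 2 footnote 8 and Section 8.1, which limit follow-up recording to medications related to adverse events. Antifungals given after an early stop must be recorded for the rule to work.

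Extending the rule to any antifungal started or added, or forcing it onto observed cultures and images, would be a trade-off rather than a correction. It would fail children switched for intolerance and override actual findings.

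The cost is SAP wording, alignment of the AC charter, one derived flag and the data-capture check in item 4. Success rates may be somewhat lower. These are scoring rules and leave treatment unchanged.
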